Analytical approaches to the analysis of data from the prevalence study will focus on univariate summaries but will also investigate risk factors for deferral, ID, and IDA. Exact confidence intervals for the probability of deferral, the probability of ID and the probability of IDA will be computed using the method first described by Clopper and Pearson. Logistic regression will be used to assess risk factors for these outcomes. For deferral, these risk factors will include age and sex but likely little else as the data we can obtain for these individuals is limited. For ID and IDA, the role of demographics will be investigated as well as other factors including socio-economic status, medical history, and diet. Final models for the impact of risk factors on deferral, ID, and IDA will include demographics and a selection of covariates found to have a statistically significant univariate association with each of these outcomes.

The analysis for the primary outcome of haemoglobin levels at 4 months will be conducted using a linear model with haemoglobin levels at 4 months as the response variable. It is unlikely that there is a need to transform the response variable as haemoglobin levels are usually symmetrically distributed with tails that decay at rates consistent with the normal distribution. However, if informal univariate assessments of normality (e.g., qq-plots) indicate strong departures from these expectations, the Box-Cox transformation will be used to select a transformation. The set of explanatory variables will be group membership (i.e.,

received iron supplementation or not), baseline haemoglobin, sex, and age. A 1-sided t-test for the regression coefficient associated with group membership will be conducted with a significance level of 0.025 to test the inferiority hypothesis. This analysis will exclude individuals who did not receive iron supplementation at baseline but received it during follow-up due to changes in ferritin or haemoglobin values. The frequency of this will be closely tracked and if more than 10% of participants in the group initially not receiving iron supplementation receive iron supplementation during follow-up, alternative analysis approaches will be considered and presented to the DSMB. At a minimum, sensitivity analyses which include those requiring iron supplementation during follow-up will be pursued. These analyses will include those requiring supplementation during follow-up in each of the 2 groups.

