**Table 1: Precision of prevalence estimates for low haemoglobin leading to deferral.**

Prevalence	Error Margin	95% Confidence Interval
0.2	0.032	0.17, 0.23
0.3	0.037	0.26, 0.34
0.4	0.039	0.36, 0.44
0.5	0.040	0.46, 0.54
0.6	0.039	0.56, 0.64

Since not all participants will consent to participate in the study and only a subset of donors are first-time donors, the precision of estimates of the prevalence of ID and IDA will be lower. Based on the unpublished estimates of the prevalence of ID and IDA provided above (i.e., 63.9% of those with anaemia had IDA and 86.1% of those with anaemia had ID, so 30.7% of the total had IDA and 41.3% had ID), estimates of the prevalence of these conditions cover almost the same range as our estimates of the prevalence of low haemoglobin. Since enrolment for this component of the study entails enrolment in the longitudinal study, the sample size was determined by the requirements for the longitudinal study which is 292 participants. Since some participants in the cross-sectional study of ID and IDA may be found to have haemoglobin (Hb)<10g/dl and will therefore be excluded from the longitudinal study, the sample size for the cross-sectional study may exceed 292. This will require that, on average, almost 2.5 participants per day consent to the study to get to about 300 over the 6-month enrolment period. Table 2 shows values for the prevalence of ID/IDA within deferral strata, the corresponding margin of error and the corresponding 95% confidence interval. For example, if the prevalence of IDA is 30% within one of the strata then a 95% confidence interval would be (25%, 35%) which has a total width comparable to the confidence intervals obtained using all potential donors. The intervals for the post-stratified estimates will be slightly larger due to the sampling variability of the estimated post-stratification weights.

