## 2.5 Framework and statistical principles

The qualitative study that precedes the trial will be used to guide implementation and evaluation of the larger study at the UH3 Phase, including identifying barriers and recommendations for using iron supplementation and nutritional counselling to increase the blood donor pool. Moreover, qualitative findings resulting from focus groups to be conducted at the end of the trial and key informant interviews will be used to guide the planning, implementation, and evaluation of the UH3 phase.

The following general principles will apply to this pilot. All confidence intervals (CIs) are 2-sided and at the 95% level and hypothesis tests are 2-sided at the 5% significance level unless otherwise specified. Percentages, means, medians and quartiles will be rounded to one significant digit. P-values will be given to 2 significant figures. Version

9.3 (or later) of SAS and/or version 3.5 (or later) of R will be used to conduct the analysis and generate tables and figures.

Descriptive statistics for enrolment rates over time and the proportion of participants completing the 6-month study visit will be assessed by treatment group. Those statistics will be used to determine the feasibility of the larger study (UH3) and may lead to changes in how consent, enrolment, and follow-up are conducted.

**Cut-date for interim reviews:** Analysis data sets will be frozen (locked) several days (or weeks) prior to the review date, to allow the statisticians time to prepare a consistent report. The cut-date may be earlier than the date of the data freeze, to allow for additional time for the reporting of events.

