### 3.4 Baseline characteristics

Baseline characteristics for those who enrol in the trial will come from information collected on the screening and enrolment forms. The only characteristics captured for those in the anaemia deferment study are age, sex, if the person has previously donated, and the type of donation (i.e., replacement/family or voluntary). For those in the study of ID/IDA information on abnormal peripheral blood film, malaria, haemoglobin, ferritin, and TTI status will also be obtained. Additional information will be available for those in the trial. For the open report, baseline characteristics will be summarized pooled across the two treatment groups and presented separately for those in the anaemia deferment study, the ID/IDA study, and the trial. Note that these study populations are related as follows: everyone in the trial is in the ID/IDA study, and everyone in the ID/IDA study is in the anaemia deferment study. Note that someone who consents to the trial but is found to have levels of haemoglobin that are too low at screening will participate in the ID/IDA study but will not participate in the trial.

For the closed report, baseline characteristics will be summarized by treatment group for the Iron Supplementation Trial.

The following baseline characteristics will be summarized with counts and percentages for binary and categorical variables, medians and quartiles for continuous variables and ordinal variables when available for each of the 3 components of the study.

Demographics:

- Age: summary as continuous variable.
- Sex.
- First-time donation status (Yes or No).
- Number of children (an integer equal or above 0).
- Marital status (6 options).
- Home situation (6 options).
- Main method of travel (private or public).
- Highest level of education completed (7 options).
- Employment category (8 options).
- Number of expensive, durable consumer items (an integer in the range 0-7).
- Ethnic background (6 options).
- Religion (5 options).

Screening laboratory results:

- Haemoglobin concentration.
- Plasma ferritin concentration.

- Malaria test results from a malaria rapid diagnostic test.
- Abnormal peripheral blood film results reported by type of abnormality (i.e., helminthic infection, malaria, neutrophilia, leucocytosis, and lymphocytosis).
- ID present
- IDA present.

Medical History:

- Diagnoses (19 options, select all that apply).

Nutritional History:

- Number of meals yesterday (4 options).

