## **7 Quantitative Data Analysis**

### **7.1 Cross-sectional study**

Analytical approaches to the analysis of data from the prevalence study will focus on univariate summaries but will also investigate risk factors for deferral. An exact

confidence interval for the probability of deferral will be computed using the method first described by Clopper and Pearson. Logistic regression will be used to assess risk factors for deferral. These risk factors will include age, sex, previous donation status and type of donor.

Since recruitment at donation events focuses on informing individuals who fail the copper sulphate test about the study, we expect that the proportions of those who are ID and IDA will be higher than the proportion among those attending a donation event. For this reason, we will estimate the level of ID and IDA overall by weighting the estimates within deferral strata by the observed probability of deferral based on the cross-sectional study of deferral (but restricted to first time donors, or voluntary first time donors depending on who enrolls into the ID/IDA study). To obtain 95% confidence intervals for the overall proportion of those who are ID and IDA we will use a Bayesian approach in which we sample the probability that first-time donors are deferred for low haemoglobin from its posterior distribution (which is a beta distribution) and we sample the probability of being ID and IDA conditional on deferral status from their posterior distributions (which will also be beta distributions). We can then combine these draws from the posterior distributions to obtain weighted estimates of the probability of being ID and IDA that will be consistent for these probabilities in the overall population. Risk factors for being ID and IDA conditional on the outcome of the copper sulphate test will be examined using logistic regression.

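### For ID and IDA the only stated model-building rule screens non-demographic covariates by univariate significance, and the SAP neither repeats it nor withdraws it

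*Protocol*

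**What the plan says.** **Protocol, Quantitative Data Analysis.** For ID and IDA, "the role of demographics will be investigated as well as other factors including socio-economic status, medical history, and diet". The list is open-ended. The paragraph closes with the rule: "Final models for the impact of risk factors on deferral, ID, and IDA will include demographics and a selection of covariates", in full "a selection of covariates found to have a statistically significant univariate association with each of these outcomes", so the covariates are those that passed a one-at-a-time significance test. It gives no threshold for that test, no closed list of candidates, and no way of choosing among those that pass. The same section describes its content as a summary, with a detailed SAP to follow.

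**SAP 7.1.** For deferral the SAP sets a closed list: "These risk factors will include age, sex, previous donation status and type of donor". For the other two outcomes there is one sentence: "Risk factors for being ID and IDA conditional on the outcome of the copper sulphate test will be examined using logistic regression". It contains no covariate list and no selection rule. The default test level, in SAP 2.5, is that "hypothesis tests are 2-sided at the 5% significance level unless otherwise specified".

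**SAP 3.4.** The baseline items include "Diagnoses (19 options, select all that apply", plus two nutritional items and eight under history of blood loss. Twelve items, including age, sex, education and employment, are listed as demographics.

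Finding the factors associated with ID and IDA is a secondary objective in both documents.

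**The concern.** Choosing covariates by univariate significance and then reporting the final model as if it had been fixed in advance has three known effects:

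- Each null candidate gets its own chance of entering.
- A factor whose effect is hidden until sex or age is adjusted for can fail the screen and not reach the adjusted model.
- A weak or uncommon factor passes only when its estimate happens to be large, so the odds ratio that is published is too large on average.

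The SAP removed the rule where it was easiest to remove, for deferral with four covariates. It left ID and IDA open, although those outcomes have many more candidates. The pilot is meant to inform the UH3 phase, so a list of risk factors that is partly chance, with some effects overstated, could steer later donor strategies. The SAP's remarks on multiplicity cover the longitudinal models (7.2.2) and the subgroup analyses (7.2.4), not these models.

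**Working it through.** **1. The plan's own figures.** The documents give no power or precision for the risk-factor models. The nearest figure for the same data is Table 2, which uses n = 292: 1.96·√(p(1−p)/292) gives 0.046, 0.053, 0.056 and 0.057 at p = 0.2, 0.3, 0.4 and 0.5, as printed. The number 292 was not chosen for risk factors: "the sample size was determined by the requirements for the longitudinal study which is 292 participants". It also suits this check, because SAP 3.4 says that the additional baseline information is available for those in the trial.

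**2. Expected events.** From the plan's prevalences, 0.48 × 0.861 = 0.413 for ID and 0.48 × 0.639 = 0.307 for IDA. In 292 donors that is 292 × 0.413 ≈ 121 ID events and 292 × 0.307 ≈ 90 IDA events. SAP 7.1 expects recruitment to favour donors who fail the copper sulphate test, so actual counts may be higher.

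**3. Chance factors.** At a two-sided 5% (the SAP default, assumed to apply to the screen), k independent null candidates give 0.05k expected admissions per outcome and probability 1 − 0.95^k of at least one.

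| k | Expected | At least one |
|---|---|---|
| 10 | 0.5 | 40% |
| 20 | 1.0 | 64% |
| 35 | 1.75 | 83% |

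The figure of 35 is a count of SAP items (19 diagnoses + 2 nutritional + 8 blood loss + 6 food and drink), not a number that the plan states. These values are near an upper bound, because a Wald test of a rare exposure rejects less often than 5%. In simulation with n = 292, a null factor passes in about 0.05–0.3% of analyses at 1% exposure, 0.6–1.5% at 2%, and about 3% at 5%.

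**4. Weak factors.** Assume 20% exposure and a true odds ratio of 1.5 for ID. Then about 58.4 donors are exposed and 233.6 are not. Risks of 0.493 and 0.393 satisfy both the odds ratio and the 0.413 prevalence.

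- Standard error of the log odds ratio: √[1/(58.4 × 0.493 × 0.507) + 1/(233.6 × 0.393 × 0.607)] = √(0.0685 + 0.0179) = 0.294.
- Smallest odds ratio above 1 that passes: exp(1.96 × 0.294) = 1.78, already above the true 1.5.
- Expected z: ln 1.5 / 0.294 = 1.379. Chance of passing: P(Z > 1.96 − 1.379) = P(Z > 0.581) = 0.28.
- Mean z given passing: 1.379 + 0.337/0.281 = 2.58. Average odds ratio when kept: exp(2.58 × 0.294) ≈ 2.1.

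Simulation over both prevalences agrees: kept in 26–28%, average (geometric mean) 2.1–2.2, and 95% interval coverage 90–92% among those kept.

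**5. Other settings (simulation, both prevalences).**

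| True odds ratio | Exposure | Kept | Average if kept |
|---|---|---|---|
| 1.5 | 10% | 17–18% | 2.6–2.7 |
| 1.5 | 30% | 33–37% | about 2.0 |
| 2.0 | 10% | 41–44% | 2.9 |
| 2.0 | 30% | 73–77% | 2.2–2.3 |
| 2.5 | 10% | 63–64% | 3.2–3.3 |
| 2.5 | 30% | 93–95% | 2.6 |

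At 20% exposure, 2.0 becomes about 2.4 and 2.5 about 2.7, with coverage of 96–97%. Without a screen, the median estimate stays close to the truth in every tabulated setting (1.49–1.52, 2.00–2.04 and 2.51–2.56).

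**6. Masking.** This is one illustrative case, with all inputs assumed: 70% men, exposure 45% in men and 15% in women, odds ratio 4 for women against men, and a true factor odds ratio of 2.0. The factor is significant in 72% of sex-adjusted models but passes the univariate screen in only 20%.

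**The case against.** The strongest reply is that the rule may no longer be in force. The protocol calls its text a summary, and SAP 7.1 rewrites that part of the plan: fixed covariates for deferral, a post-stratified Bayesian interval for ID and IDA, and risk-factor models conditional on the copper sulphate result. Deliberate replacement is plausible. But SAP 1.2 presents the SAP as adding statistical detail beyond the protocol, and SAP 7.1 does not say that the screen is dropped. If it has been dropped, ID and IDA have no covariate list and no rule, and the remedy is the same.

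Four further replies limit the size of the point, and they stand:

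- **Demographics are not screened.** A reader might infer that the whole model is filtered. It is not: age, sex and the socio-economic items that SAP 3.4 lists as demographics enter regardless.
- **The candidate pool is uncertain.** A reader might infer that more than one chance factor is to be expected, in over 80% of analyses. That needs about 35 independent, reasonably common candidates. The six food and drink items come from the copper sulphate comparison in SAP 7.2.2, nothing makes each diagnosis a separate covariate, and donor screening will make several conditions rare.
- **Inflation and undercoverage are not general.** A reader might infer that all reported intervals are too narrow. At 20% exposure that holds for an odds ratio of 1.5 but not for 2.0 or 2.5.
- **Low power is not cured.** The 26–28% is essentially the power of a single test at this sample size. A fixed list would not make a weak factor much easier to detect; it would stop the report from depending on whether the factor was detected.

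**Conclusion.** The point holds as a minor one. The only model-building rule stated for ID and IDA is a univariate-significance screen on non-demographic covariates, and the SAP leaves its status unclear. If applied, it can admit chance factors (at most about 0.05 per candidate), miss masked factors, and inflate weak or uncommon effects: 1.5 becomes about 2.1–2.2 at 20% exposure and 2.6–2.7 at 10%. For stronger and commoner factors the distortion is small.

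These sizes rest on n = 292, a 5% two-sided screen, independent null candidates, and exposure frequencies and odds ratios that the documents do not give. A looser threshold would lose fewer real factors and admit more chance ones. The documents do not support a claim that the published list will be mostly chance findings, or that the trial's main conclusions are at risk. The non-inferiority test and the prevalence estimates do not use these models.

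**What to change.** In SAP 7.1, state that the protocol's univariate screen is not used for ID and IDA, and align the protocol sentence. Before database lock, name a short covariate list and say which demographics are meant. Size the list to about 121 ID and 90 IDA events; 35 candidates would leave only 121/35 ≈ 3.5 and 90/35 ≈ 2.6 events each. Enter the list together with age, sex and copper sulphate result. Use Firth logistic regression if events are sparse; ridge would not supply standard confidence intervals. Report every odds ratio with its interval, significant or not. Factors left off the list can still be described univariately and labelled exploratory.

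The cost is SAP wording and one agreed list, with no new data; SAP 1.1 allows updates until database lock. The downside is that fewer factors are examined in the adjusted model and intervals are somewhat wider.
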